	
- PRO measures (POEM, DLQI, CDLQI, peak pruritus NRS, and quality of sleep NRS)- Lipidomics in STS (ratio of EOS CER to NS CER)- Filaggrin breakdown products of UCA and PCA concentrations in STS- Key components of skin proteomics in STS (expression of proteins associated with skin barrier function)- Key components of gene expression from transcriptomics- Image-derived severity score in targeted lesional skin• Correlation between percent change from baseline in TEWL before STS and TEWL AUC in lesional and non-lesional skin of AD patients at Week 8 and Week 16 with corresponding change from baseline in the following measures:
- Local target lesion erythema and edema/papulation; ISS- EASI, SCORAD- PRO measures (POEM, DLQI, CDLQI, peak pruritus NRS, and quality of sleep NRS)- Lipidomics in STS (ratio of EOS CER to NS CER)- Filaggrin breakdown products of UCA and PCA concentrations in STS- Key components of skin proteomics in STS (expression of proteins associated with skin barrier function)- Key components of gene expression from transcriptomics- Image-derived severity score in targeted lesional skin

Overall design:

- Phase IV.
- Two study sites ([name], Denver, USA; [name], Innovaderm, Montreal, Canada).
- Open-label, exploratory study.
- Approximately 24 patients with moderate to severe AD will be enrolled to achieve 20 evaluable patients.
- Approximately 24 evaluable healthy volunteers matched for age, gender, location of skin area, and study site will serve as a reference comparator for skin barrier function.

This is a 16-week, open label, exploratory study designed to investigate dupilumab's effect on skin barrier function as measured by TEWL before and after skin tape stripping in approximately 10 adolescent and approximately 10 adult patients with moderate to severe AD (not more than 12 of either group). During the first 2 treatment weeks, patients will have 2 on-site visits/week, followed by one on-site visit/week up to Week 4, one on-site visit every two weeks from Week 4 to Week 8, and one on-site visit every 4 weeks up to Week 16 End of Treatment phase visit (EoT) thereafter.

A follow-up visit by phone 4 weeks after the last study assessment at Week 16 will end the study for each participant (End of Study: EoS). The maximum duration of the study per participant will be 24 weeks.

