Lesional and non-lesional skin areas for TEWL assessment and STS will be identified on the upper limbs or lower limbs at baseline ("predefined skin area"). TEWL and STS-assessment at pre-defined non-lesional (normal looking) skin area in AD patients should be made about 4 cm from the edge of the lesional area.

Within the predefined lesional skin (LS) and non-lesional skin (non-LS) areas three closely adjacent spots will be identified for subsequent skin barrier function assessment (3 spots on lesional skin, 3 spots on non-lesional skin). These spots must not overlap with each other once skin tapes are applied.

The skin barrier function without and before STS will be assessed using TEWL measurement on each of the three spots within these pre-defined skin areas at each visit.

Repeated TEWL assessment in pre-defined lesional and non-lesional skin areas of AD patients after STS for lipidomics, proteomics and transcriptomics analysis in STS samples will be conducted at baseline (Week 0, Day 1), Week 2 (Day 15), Week 4 (Day 29), Week 8 (Day 57), Week, 12 (Day 85), and at EoT at Week 16 (Day 113).

In order to allow the skin to recover from the STS, the skin barrier function assessment with STS will be performed as follows: STS assessment on baseline (Week 0), Week 8 and Week 16 will be conducted on the first spot within the predefined lesional and non-lesional skin area. STS assessment on Week 2 will be conducted on the second spot. STS assessment on Week 4 and Week 12 will be conducted on the third spot.

TEWL will be measured before and after 5, 10, 15, and 20 STS (5 TEWL assessments per visit) on targeted, predefined lesional, non-lesional skin in AD patients at baseline, Week 2, Week 4, Week 8, Week 12, and Week 16 on the predefined first, second or third spot, respectively.

Skin barrier function in approximately twenty healthy volunteers matched for age, gender, location of targeted lesion area, and study site to the AD cases will be assessed in a similar manner at baseline, twice a week during the first two weeks, once a week during Week 3 to Week 4, every two weeks from Week 4 to Week 8, and every four weeks up to Week 16 thereafter, serving as a reference comparator for skin barrier function.

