- g* Peak pruritus NRS and quality of sleep NRS will be assessed daily from Day-7 to Day -1; daily from Day 1 to Day 29 and then for the 7 days prior to Week 6, Week 8, to Week 12 and to Week 16 by e-diary. Patients will bring the eDiary to the site at each visit. eDiary will be reviewed for any questionnaires omission and dispensed back to patients at each visit.
- h* TEWL to be conducted before STS and then after 5, 10, 15, and 20 STS in pre-defined lesional and non-lesional skin. All skin tape strips will be collected and stored.
- i* At Week 0, 8 and 16 STS will be conducted on the first spot within the predefined skin area. At Week 2 STS will be conducted on the second spot within the predefined skin area. At Week 4 and 12 STS will be conducted on the third spot within the predefined skin area. TEWL will be assessed in lesional and non-lesional skin before STS and after 5, 10, 15, and 20 STS. All skin tape strips will be collected and stored for lipidomics, proteomics, and transcriptomics analyses.
- j* Emollients should NOT be applied from Day -7 to the EoT (Week 16, Day 113) to the targeted, pre-defined skin areas that will be used for TEWL assessment. Participants should not take showers or soaking in a bathtub within 6 hours before TEWL assessment. Compliance must be documented in participant's source data. Emollients for use during the study will be provided by the study site to study participants. Use of emollients should be documented in a diary.
- k* Limited to skin-related physical examination at baseline and EoT visit.
- l* Pre-defined lesional (3 spots) and non-lesional skin areas (3 spots), whereby the assessment spots on non-lesional skin are located about 4 cm apart from the edge of the AD lesion.
- m* TEWL will be measured at each of the three closely adjacent spots within the predefined skin areas at all visits as baseline assessment; if there is STS, subsequent TEWL assessment will only be done at the lesional and no-lesional spot, at which STS is performed.
- n* In case STS assessment is to be conducted at an unscheduled visit or at a premature end of treatment visit the assessment should be conducted at that spot of the skin area, for which the period passed since the last STS assessment is the longest.

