9.4.7.1 Description of efficacy variables

Efficacy parameters are described in [Section 8.2](#). The derivation of baseline results is described in [Section 9.4.4.2](#).

The analysis of the efficacy marker will be based on the mITT population. As a sensitivity analysis, the primary endpoint will also be analyzed based on the ITT population. Secondary endpoints analysis might be run on the ITT population as sensitivity analysis in case an important number of patients using rescue therapy is observed.

Sub-analysis might be done for adolescents and adults, if deemed appropriate.

TEWL data collected at the same visit from without and before STS measurement on each of the three spots within the predefined skin areas will be averaged, unless a large difference between spots is observed.

Analysis

Table 4 - Efficacy analyses

Endpoint	Statistical Analysis Methods
Primary	
Percent change from baseline in TEWL after 5 STS assessed on lesional skin at Week 16 in AD patients	
Raw data and change from baseline; ie, absolute and percentage changes, will be summarized with descriptive statistics (such as mean, median, SD, minimum, and maximum) based on the mITT and ITT populations.
 
Profiles for baseline and Week 16 time points will be generated for individual values: eg, spaghetti plot and boxplot, and patients' cohort means.
 
For information purpose as study is not powered (no multiplicity correction will be applied):
 
Difference between baseline and Week 16 values will be tested through one-sided paired t-test at a Type 1 error level of alpha=0.05 ($H_0: 0 \leq TEWL_{Week16} - TEWL_{baseline}$, $H_a: 0 > TEWL_{Week16} - TEWL_{baseline}$).
 
Point estimate, two-sided 90% confidence interval and corresponding one-sided p-value will be reported.
 
If assumption of normal distribution is strongly violated, non-parametric methods: eg, Wilcoxon signed-rank test, will be used; normality assumption will be assessed through quantile-quantile plot and Shapiro-Wilk test at 5% Type I error.

Endpoint	Statistical Analysis Methods
Secondary	
Change (percent and absolute) from baseline in TEWL after 20 STS assessed on lesional skin at Week 16 in AD patients	The similar approach as for the analysis of primary endpoint will be used.

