Change (percent and absolute) from baseline in TEWL after STS assessed on lesional skin in AD patients over time	As exploratory analysis time to improvement of skin barrier function for lesional and non-lesional skin area measured by TEWL will be summarized. Improvement is defined as time to the first post-baseline day for which at least one TEWL measure of a patient is equal or lower than the median, of the corresponding TEWL measured in his/her matched healthy volunteer over time. Results might be reported through Kaplan-Meier plot.
Change (percent and absolute) from baseline in TEWL after STS assessed on non-lesional skin in AD patients over time	
Change (percent and absolute) from baseline in TEWL after STS assessed on normal skin in healthy volunteers over time	
Change (percent and absolute) in TEWL area under the curve (TEWL AUC: a composite measure before and after 5, 10, 15 and 20 STS) for skin barrier function in lesional skin in AD patients over time	As all TEWL values are expected to be positive, area under the TEWL curve will be calculated using the trapezoidal method over the 10 or 20 STS (measurement at every five STS) at each visit.
Change (percent and absolute) in TEWL area under the curve (TEWL AUC: a composite measure before and after 5, 10, 15, and 20 STS) for skin barrier function in non-lesional skin in AD patients over time	Raw data and change from baseline; ie, absolute and percentage changes, will be summarized with descriptive statistics (such as mean, median, SD, minimum, and maximum) by groups and time points.
Change (percent and absolute) in TEWL area under the curve (TEWL AUC: a composite measure before and after 5, 10, 15, and 20 STS) for skin barrier function in normal skin in healthy volunteers over time	Profiles over study days will be generated for individual values and group means for raw data and absolute change from baseline.
	Percentage change relative to the healthy volunteers' cohort will be calculated as a ratio of means by time point for lesional and non-lesional skins groups.
	As exploratory analysis time to improvement of skin barrier function for lesional and non-lesional skin area measured by TEWL AUC will be summarized. Improvement is defined as time to the first post-baseline day for which TEWL AUC of a patient is equal or lower than the median, of the corresponding TEWL AUC computed in his/her matched healthy volunteer over time. Results might be reported through Kaplan-Meier plot.
Tertiary/exploratory	

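### The exploratory time-to-improvement rule accepts one unconfirmed crossing at any TEWL depth, with five chances at stripping visits and one at the others; the size of the effect depends on variability the plan does not give

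*Protocol*

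**What the plan says.** The rule is in Protocol Section 9.4.7.1, Table 4, in the rows for TEWL over time. The reference is the matched volunteer's own median at the same depth. The rule reads: "Improvement is defined as time to the first post-baseline day for which at least one TEWL measure of a patient is equal or lower than" that reference. Nothing in the rule asks for a second reading, a minimum number of depths or a later visit to agree.

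The number of readings differs by visit:

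- **Stripping visits.** The Synopsis says "TEWL will be measured before and after 5, 10, 15, and 20 STS (5 TEWL assessments per visit"), and this applies "at baseline, Week 2, Week 4, Week 8, Week 12, and Week 16 on the predefined first, second or third spot, respectively". Five of these six visits are post-baseline.
- **All visits.** TEWL before stripping "will be assessed using TEWL measurement on each of the three spots within these pre-defined skin areas at each visit". Section 9.4.7.1 reduces this to one value per area, because the "measurement on each of the three spots within the predefined skin areas will be averaged, unless a large difference between spots is observed".
- **After stripping starts.** Footnote m to the schedule in Section 1.3 says "if there is STS, subsequent TEWL assessment will only be done at the lesional and no-lesional spot, at which STS is performed". At visits without stripping there are therefore no post-STS readings.

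The analysis is labelled exploratory and the Kaplan-Meier plot is optional. Table 4 also plans a parallel time to improvement on TEWL AUC, with one value per stripping visit. SAP Section 1.2 does not alter the rule. SAP Section 1.3 fills missing TEWL by LOCF.

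**The concern.** A patient who is above the volunteer's median at four depths and just below it at the fifth counts as improved from that day, whatever follows. Taking the lowest of several noisy readings relative to their references makes a chance crossing more likely, and the rule takes five readings at some visits and one at others. Two visits with the same true barrier state can therefore have different chances of producing an event.

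What is at stake is how the curve is read. The time course of barrier improvement is a secondary objective (Section 3, Table 1), and the study has no untreated AD arm (Section 6.3). A Kaplan-Meier curve of patients reaching a healthy reference is easily taken as a treatment effect, although part of it could come from measurement noise and the timing of stripping visits.

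**Working it through.** **Inputs from the documents.** The post-baseline on-site visits in Section 1.3 are Days 4, 8, 11, 15, 22, 29, 43, 57, 85 and 113. Days 15, 29, 57, 85 and 113 are stripping visits with five depths; the other five visits have one pre-STS value. Section 9.2 plans 20 evaluable patients (20/0.85 = 23.5, rounded up to the stated 24 enrolled). It also says that TEWL data from similar settings were not available. The plan states no event rate for this analysis, so there is no such figure to reproduce.

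**Chances per skin area.** 5 visits × 5 depths + 5 visits × 1 = 25 + 5 = 30.

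**Assumptions.** The patient does not change. The true level is k within-patient SDs above the reference, errors are normal, visits are independent, and the depths within a visit are correlated 0.3 to 0.8. The values of k and the correlation are assumed, so a range is shown.

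**Check by formula at k = 2.** One reading crosses with probability Φ(−2) = 2.28%. With pre-STS TEWL only, the chance of at least one crossing in 10 visits is 1 − 0.9772^10 = about 20.6%. With 30 independent readings it is 1 − 0.9772^30 = about 50%. Correlation within visits brings the rule as written below that ceiling.

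**Simulation, equal gap at every depth (200,000 patients per setting).**

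| Gap k (SDs) | Rule as written, by Week 16 | Pre-STS only |
|---|---|---|
| 1.5 | 68-83% | 50% |
| 2 | 34-46% | 20-21% |
| 2.5 | 12-16% | 6% |
| 3 | 3-4% | 1% |

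At k = 2, 34-46% of 20 patients is about 7 to 9. At k = 3 it is fewer than one (20 × 0.04 = 0.8). At k = 2, 69-78% of first events fall on stripping visits, which are half of the visits.

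**Gap widening after stripping.** With k = 2 before stripping and k = 3 at all four post-STS depths, the rule as written gives 21-22%, against 21% for pre-STS only. First events on stripping visits are then 49-52%, so there is no clustering. With gaps of 2, 2.5, 3, 3 and 3, the figures are 22-24% and 50-56%.

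**Noise in the volunteer's median.** The reference is one volunteer's own median, from 11 planned pre-STS values or 6 planned values at each post-STS depth. A second simulation (40,000 pairs per setting, equal gaps, correlation 0 to 0.95) lets that median vary. False events are 34-61% at a 2-SD gap and 4-8% at 3 SD. At 2 SD and correlation 0.5, the rule as written gives 50%, pre-STS only 24%, AUC 4.5%, and pre-STS confirmed at the next visit 1.3%.

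**The case against.** The strongest reply is that little depends on this analysis. No hypothesis test is predefined (Section 9.1), time to improvement is not a listed endpoint in Table 1, and the plot may not be produced. The planned AUC version has no any-depth rule. Table 4 also requires summaries by number of STS and time point, and individual profiles, in which an isolated crossing would be visible. All of this stands and limits the point to minor. It does not cure the rule: followed exactly, the rule can record improvement when nothing has changed, and the AUC version is unconfirmed too.

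A reader might infer that the steps of the curve must gather at stripping visits. The documents do not support that. Section 3.1 says healthy skin tolerates mild stripping while disrupted skin shows larger TEWL changes. If so, the patient-volunteer gap may widen with depth, and the clustering then disappears. If the noise grows in proportion to the gap, clustering returns. The documents cannot settle which applies.

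A reader might also infer that a third to a half of the patients would be falsely improved. That holds only near a 2-SD gap. Inclusion criterion I 06 requires a lesion score of at least 2 for erythema or edema/papulation, so a larger gap is plausible in lesional skin. The risk is more plausible in non-lesional skin or late in treatment.

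Mandatory confirmation is not clearly right either. Intervals to the next visit run from 3 to 28 days, consecutive stripping visits use different spots, and discarding first crossings at Week 16 would lose real late improvement. These are reasons to make confirmation a sensitivity analysis.

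**Conclusion.** The point holds as a minor fault in a stated rule. The any-depth, single-crossing definition and the uneven 25 + 5 split of chances are in the text, and the SAP leaves them in place. Under a no-change model with equal gaps, false improvement by Week 16 ranges from about 3% at a 3-SD gap to 83% at 1.5 SD. If the gap is 2 SD before stripping and 3 SD after, the any-depth rule adds almost nothing to the 21% that comes from unconfirmed pre-STS crossings alone. These figures rest on assumed gaps, equal and normal noise, independent visits and, in the main simulation, an error-free reference. They show what the rule can do and do not predict this study's result. The primary endpoint and its paired test are untouched.

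**What to change.** In Table 4, or in the SAP as a stated modification:

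1. Drop the any-measure wording and define the event separately for each measure. Use pre-STS TEWL, available at all visits, for the main curve and after-5-STS TEWL, at stripping visits only, for a separate curve. Keep the planned AUC curve.
2. Define events from observed values only. A value carried forward by LOCF adds no new evidence and would confirm its own crossing.
3. Add a sensitivity analysis in which a crossing counts only if an observed value at the next scheduled measurement of the same measure is also at or below the reference. Report first crossings at Week 16 separately as unconfirmed.

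The cost is SAP wording and a little more programming, with no new data. The downside is fewer events, most of all in the confirmed analysis.

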3.1 APPROPRIATENESS OF MEASUREMENTS

The primary endpoint is percent change from baseline in TEWL after 5 tape strips assessed on lesional skin at Week 16 in AD patients, and key secondary endpoints include TEWL changes over time measured by TEWL AUC after various number of STS. The stratum corneum (SC) provides skin barrier protection and controls transcutaneous water loss. TEWL measurement, which quantifies water diffusion across the SC, is commonly used for the physiologic assessment of skin barrier function (18). In addition to basal TEWL to assess the undisturbed permeability of the skin barrier, TEWL measurements have also been conducted together with controlled skin barrier perturbation using skin tape stripping (STS) to measure skin barrier integrity (7). Healthy skin is not highly sensitive to STS, and can withstand mild perturbation, while disrupted skin and skin with low structural integrity exhibit greater changes in TEWL. The area under the curve (AUC) for TEWL measurements (TEWL AUC) done over a defined number of STS is used to reflect the overall integrity of the SC. Skin barrier dysfunction and increased TEWL are major pathologic features of AD (14, 19, 20). TEWL has been shown to correlate with AD severity (21, 22, 23). Therefore, this study has selected TEWL in conjunction with STS, and TEWL AUC as the key primary and secondary endpoints.

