5.1 INCLUSION CRITERIA

Participants are eligible to be included in the study only if all of the following criteria apply:

Age

- I 01. Participant must be between 12 to 65 years of age (inclusive), at the time of signing the informed consent.

Type of participant and disease characteristics

Atopic dermatitis patients and healthy volunteers:

- I 02. Male or female patients.
- I 03. Patients with AD diagnosis according to Hanifin and Rajka criteria at least 1 year before screening. (AD patients only)
- I 04. Investigator Global Assessment (IGA) score of ≥ 3 at screening (on the 0-4 scale). (AD patients only)
- I 05. Patients with moderate to severe atopic dermatitis that are eligible to be treated with dupilumab according to product monograph. (AD patients only)
- I 06. Patients with AD must have active lesions on the upper limbs or lower limbs, with severity for lesion erythema or edema/papulation ≥ 2 at screening on the 0-3 scale of the ISS. (AD patients only)
- I 07. Participants should have a non-lesional (normal looking) skin area 4 cm from the edge of the lesional area. If unable to identify non-lesional skin 4 cm from the lesional area, it is acceptable to identify normal looking skin as close to the lesion as possible. (AD patients only)
- I 08. Willing to refrain from applying any topical medication products on the target assessment areas (including lesional and non-lesional) throughout the study until the EoT visit unless necessary to alleviate intolerable symptoms.

- I 09. Willing to refrain taking showers or soaking in a bathtub with soaps and body washes within 6 hours before TEWL assessments.
- I 10. Willing to NOT apply any moisturizers to the areas of the skin that are targeted assessment areas (lesional and non-lesional) during the entire study from Day -7 to the EoT visit.
- I 11. Willing and able to comply with all clinic visits and study-related procedures.

Healthy volunteers only:

- I 12. Age and gender matched to a selected AD patient by study site. Adolescents aged 12 to 17 years will be matched by post puberty status, and adults aged 18 to 65 years will be matched by age as close as possible within 10 years of age.
- I 13. No current dermatologic or systemic condition that could interfere with the assessments.

Weight

Not applicable.

Sex

- I 14. Male or Female

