6.3 MEASURES TO MINIMIZE BIAS

The study is open label study without a treatment control group in patients. To control bias, the following measures are taken:

- Age-, gender-, targeted lesion area-, and study site-matched healthy volunteers will serve as a reference comparator cohort for interpreting study results.
- PROs will be collected by electronic data capture.
- Efficacy data (TEWL) will be measured by the same device model.
- Biomarker data (lipidomics, proteomics, and transcriptomics) will be measured by an experienced, central laboratory.
- Study is limited to 2 very experienced study centers
- One central laboratory for lipidomics, proteomics and transcriptomics analyses to reduce skin barrier assessment variabilities.
- Standardized study assessment procedures, including TEWL and STS skin barrier function
- Standardized photography for targeted lesional and non-lesional areas, and clinical disease severity and patient reported outcome evaluations.
- Reason for screen failures (if any) will be documented.

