8.2 EFFICACY ASSESSMENTS

8.2.1 Transepidermal water loss assessment and skin tape stripping

8.2.1.1 Transepidermal water loss assessment

Transepidermal water loss is a skin barrier function test that measures perspiration or water loss through the skin. Transepidermal water loss is generally higher in AD skin compared to normal skin as the barrier is disrupted allowing water to evaporate more readily. If the barrier improves with dupilumab treatment, TEWL would be expected to decrease.

TEWL assessment will be conducted in a quiet environment with temperature and humidity being documented. TEWL measurements will be conducted in the same room throughout the study where possible. Subjects will be acclimated to the room for a minimum of 20 minutes prior to TEWL measurements. Room temperature will be set to be within 19.0°C to 23.0°C. Humidity will be set to be below 60% as the maximum allowed humidity. To further control TEWL readout, moisturizers will be standardized for all study participants starting from Day -7 until Day 113 (Week 16). The first TEWL assessment at each visit will be conducted at each of the three spots in predefined lesional and non-lesional areas respectively. After start of STS all subsequent TEWL assessments at each visit will be done on the single lesional and non-lesional spot respectively at which the STS is performed (see also [Figure 3](#)).

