8.2.1.2 Skin tape stripping and collection of skin tapes

In addition to TEWL measurements at the skin surface, TEWL measurements can be combined with STS to measure skin barrier function. With STS, the uppermost layers of the skin are peeled away using adhesive discs. Skin with compromised skin barrier exhibits greater changes in TEWL. The area under the curve for TEWL measurements over a defined number of STS reflects the overall function of the SC.

This procedure involves the defined, non-invasive application of a commercially available adhesive sheet on the surface of the skin at predefined areas. A dedicated instrument (eg, D-SQUAME Pressure Instrument D500) is used to apply a defined pressure onto the skin tape strip for 5 to 10 seconds. Thereafter the skin tape strip will be peeled off the skin in a ripping motion using a forceps (= the skin tape-stripping method).

This procedure will be repeated up to 20 times sequentially, interrupted every 5 STS by TEWL to collect samples from the stratum corneum. The samples will be collected for lipidomics, proteomics and transcriptomics assessment.

[figure not shown]
Lesional and non-lesional areas of skin will be tested. Patients will undergo skin barrier function tests at time points according to [Section 1.3](#) before, and after skin tape stripping.

Healthy volunteers will undergo skin barrier function tests at time points according to [Section 1.4](#) before, and after skin tape stripping.

Specifically, lipidomic, proteomic and transcriptomics samples will be collected by STS at baseline, Week 2, 4, 8, 12, and 16. A total 240 skin tapes will be collected in lesional, non-lesional or normal skin, respectively.

[figure not shown]
In order to allow the skin to recover from STS three closely adjacent spots (without an overlap for the skin tapes) will be identified for subsequent skin barrier function assessment within lesional, non-lesional and normal skin area ([Figure 2](#)). STS assessments from the same spot will be separated by 8 weeks. In case of STS assessment at an unscheduled visit or at a premature end of treatment visit the assessment should be conducted at that spot of the skin area, for which the time period passed since the last STS assessment is the longest.

Figure 2 - Example of selection of skin spots within lesional and non-lesional skin

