9.1 STATISTICAL HYPOTHESES

No hypothesis testing is predefined in this exploratory study.

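### Time to improvement has no Day 1 condition, so a patient already at the volunteer's level, with unchanged skin, counts as improved

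*Protocol*

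**What the plan says.** Table 4 in protocol section 9.4.7.1 plans an exploratory time-to-improvement summary for lesional and non-lesional skin, in two versions. For TEWL the event is the "first post-baseline day for which at least one TEWL measure of a patient is equal or lower than the median" of the corresponding values of the matched healthy volunteer over time. For TEWL AUC it is the "first post-baseline day for which TEWL AUC of a patient is equal or lower than the median" of the volunteer's AUC values. A Kaplan-Meier plot is optional; the summary itself is not.

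On what improvement means, section 8.2.1.1 says: "If the barrier improves with dupilumab treatment, TEWL would be expected to decrease".

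No entry rule is based on TEWL. In section 5.1, lesional skin qualifies on an erythema or edema/papulation score (I 06) and non-lesional skin on appearance: "Participants should have a non-lesional (normal looking) skin area 4 cm from the edge of the lesional area" (I 07, which allows a closer site if needed).

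Section 9.4.4.2 defines a Day 1 baseline for TEWL, but the event rules do not use it. SAP section 1.2 ties change scores to Day 1 at the same number of strips. Neither SAP section 1.2 nor 1.3 mentions time to improvement.

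**The concern.** Improvement is a change within a patient, but both rules test only a level: is the patient at or below one volunteer's median? Someone who was there on Day 1 satisfies the rule with unchanged skin, or even slightly worse skin if still under the median. Such events fall mostly at the earliest assessment (Day 4 for TEWL before stripping, Day 15 for AUC), so a Kaplan-Meier curve would show them as rapid onset.

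Non-lesional skin is the likeliest place for this, because the site is chosen to look normal. That is an inference; section 2.2 says barrier changes are already present there. The threshold also comes from a single volunteer, so a volunteer with high TEWL makes Day 1 qualification easier.

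Section 6.3 states: "The study is open label study without a treatment control group in patients". Nothing in the design therefore shows how often untreated patients would meet the rule. At stake is a count of improved patients that supports the secondary time-course objective.

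**Working it through.** **The plan's own figure.** The event rule has none. The only related number is the sample size in section 9.2: 20 / (1 - 0.15) = 23.5, rounded up to 24 enrolled for 20 evaluable. This reproduces. The examples below use 20 patients.

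**Step 1: the wording alone.** Let T_k(t) be the patient's TEWL after k strips at visit t, and m_k the volunteer's median over visits at the same k. The rule is: event if T_k(t) <= m_k for some k at some t after Day 1. With unchanged skin and no measurement noise, T_k(t) = T_k(Day 1). The event then occurs exactly when T_k(Day 1) <= m_k for some k, so every Day 1 qualifier is an improvement and nobody else is.

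**Step 2: how many patients qualify on Day 1, without noise.** Assumptions: log-normal TEWL, between-person log SD s = 0.35, patient/volunteer ratio R, matching correlation r. The share is Phi(-ln R / (s * sqrt(2(1 - r)))).

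| R | r = 0 | r = 0.5 |
|---|---|---|
| 1.2 | 0.182/0.495 = 0.368, so 36% | 0.182/0.35 = 0.521, so 30% |
| 2 | 0.693/0.495 = 1.400, so 8% | 0.693/0.35 = 1.980, so 2% |
| 3 | 1.099/0.495 = 2.220, so 1% | 1.099/0.35 = 3.139, so 0.1% |

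**Step 3: simulation with visit noise and no treatment effect.** The schedule follows section 1.3: Day 1 plus 10 later visits with a reading before stripping, and readings after 5, 10, 15 and 20 strips on Day 1 and at Weeks 2, 4, 8, 12 and 16. There were 60,000 pairs per setting. All other inputs are assumptions:

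- Log SDs (subject/visit/reading) of 0.35/0.20/0.12 as base, varied to 0.25/0.15/0.10 and 0.45/0.30/0.15.
- Matching correlation 0 (base) or 0.5.
- Volunteer TEWL rising over strips as 1, 1.15, 1.35, 1.6, 1.9, with the patient's log rise 1 (base), 1.5 or 2 times that.

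Ranges cover all 18 settings per ratio.

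| TEWL rule as written | R = 1.2 | R = 2 | R = 3 |
|---|---|---|---|
| Called improved by Week 16 | 70% (61-82%) | 32% (7-46%) | 11% (0-25%) |
| Of those, already met the rule on Day 1 | 68% (44-68%) | 48% (16-51%) | 36% (base only) |
| Of those, no crossing reading below the patient's own Day 1 reading | 26% (19-28%) | 16% (6-20%) | not tabulated |

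With correlation 0.5 and equal rise, the Day 1 shares are 62% and 34% at R = 1.2 and 2.

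For the AUC rule, with patient rise 1, 1.5 and 2 times the volunteer's, the improved share is 55, 41 and 28% at R = 1.2 (range 10-64%) and 19, 12 and 6% at R = 2 (0-32%).

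In 20 patients at R = 1.2: 0.70 x 20 = 14 called improved, and 0.68 x 14 = 9.5 of them already met the rule on Day 1. At R = 2: 0.32 x 20 = 6.4, and 0.48 x 6.4 = 3.1.

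**Step 4: what a Day 1 condition removes.** With no noise, it removes every false event. With noise, and using the pre-strip reading, 43-53% of the remaining at-risk patients still cross with unchanged skin at R = 1.2 (range 41-61%), and 16-18% at R = 2 (6-30%). The condition cures the titled defect, not chance crossings.

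**The case against.** The strongest reply is about size. The base case assumes no patient-volunteer correlation and an equal rise over strips, yet volunteers are matched on age, gender, skin location and site, and the protocol expects damaged skin to react more: "disrupted skin and skin with low structural integrity exhibit greater changes in TEWL" (section 3.1). With correlation 0.5 and a rise of 1.5 to 2, Day 1 qualifiers fall to 51-54% of events at ratio 1.2 and 26-28% at ratio 2, where about 1 patient in 20 meets the TEWL rule on Day 1. This stands: the base Day 1 shares sit at or near the top of their ranges. These settings still lie inside the stated ranges.

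Second, the 70% mixes two things: the missing Day 1 condition and first-crossing noise. This also stands; the Day 1 share, not the 70%, measures the defect.

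Third, section 8.2.1.1 states an expectation and does not define an event, and it also says TEWL is usually higher in AD skin. That is fair, and it is why lesional skin is probably little affected. The rule still labels as improvement something that needs no fall.

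Fourth, individual profiles, change scores and ratios to volunteers are reported alongside, and section 9.1 says: "No hypothesis testing is predefined in this exploratory study". This limits the consequences, but those displays do not correct a count of improved patients.

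**Conclusion.** The concern holds. Both definitions count an unchanged patient who starts at or below the reference as improved, and no other section prevents it. This follows from the wording and needs no assumption.

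The size does need assumptions. With no treatment effect, Day 1 qualifiers make up 44-68% of TEWL-rule events at a patient/volunteer ratio of 1.2 and 16-51% at a ratio of 2. Where lesional TEWL is clearly raised, few patients are affected. The documents supply neither ratios nor SDs, so these figures are illustrations, not predictions.

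The consequences are limited: the analysis is exploratory and carries no test, and the primary and change-from-baseline endpoints are unaffected. The definition should be changed, but it does not threaten the trial's main result.

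**What to change.** In Table 4 and the SAP:

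1. Restrict each time-to-event analysis to patients whose Day 1 value of the same measure (TEWL at that number of strips, or AUC) is above the matched volunteer's median. If any single TEWL reading may still trigger the event, every Day 1 reading must be above its own reference.
2. Report, by skin area, how many patients were at or below the reference on Day 1.
3. Call the event time to normalisation, and state beside it that chance crossings and regression to the mean remain, so it is not evidence of a drug effect by itself.

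Possible wording for one named measure: *Among patients whose Day 1 value exceeds the matched healthy volunteer's median over time for the same measure, time to the first post-baseline day at or below that median; patients at or below it on Day 1 are counted separately by skin area.*

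Optional: use one named reading in place of any reading, and add a sensitivity version confirmed at the next visit.

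The cost is SAP wording and a small programming change; all data are already collected. The risk set shrinks, mainly for non-lesional skin. Under the base assumptions, about 13 of 20 patients remain at ratio 1.2 and 18 of 20 at ratio 2 for a single reading, or about 10 and 17 if every Day 1 reading must be above its reference. Selecting on a high Day 1 value also introduces regression to the mean, which is why the caution in step 3 is needed.
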